### 3.4 Data Collection

We will use several qualitative and quantitative assessments during the usability testing of the veteran student app, *VetEd* (Phase 2, see Table 3 below).

**Table 3. Veteran Completed Assessments for the Evaluation of *VetEd***

Measure*	Screen	Baseline	Midpoint	Post-App Follow-up	Purpose
Demographics	X	X			Eligibility, Sample Description
SCID-5		X			Eligibility, Sample Description
PCL5		X		X	Sample Description
PHQ-9		X		X	Sample Description
SUS			X	X	Usability
AES			X	X	Feasibility, Acceptability, Usability
ASES		X	X	X	Academic Outcome
CWBS		X	X	X	Academic Outcome
M2C-Q		X		X	Community Reintegration Outcome
Post-App Interview				X	Usability Feedback & Academic Outcomes

\*Note. Full names and descriptions of measures are listed below.

**Demographics, functional health, and pain measures.** Demographic measures will include age, gender, race and ethnicity, and education. These measures will take approximately 10 minutes.

**Mobile App Utilization.** We will collect information on *VetEd* usage, including the duration of use (minutes), number of logins, completion of in-app activities, and the percentage of participants who complete the program.

**Mental Health Symptom Measures.** To assess for important psychological co-morbidities in chronic pain treatment, we will administer the 9 - item Patient Health Questionnaire-9 (PHQ-9) to assess for depressive symptoms, and 20-item PTSD Checklist-5 (PCL-5). These surveys will take approximately 7 minutes.

**Mental Health Diagnostic Measure:** The *Structured Clinical Interview for the DSM (SCID-5)* is a reliable semi-structured instrument that is the gold standard for diagnosing mental health disorders. The utilized SCID modules will take approximately 30 minutes.

**System Usability Scale (SUS):** The SUS is a 10-item measure, scored on a 5-point Likert scale, that assesses human-computer interaction. A SUS score above 58 is regarded as above average, and a SUS score above 80 is regarded as high and a score above which participants are likely to recommend the product to friends. The SUS generates a subjective evaluation score using a globally accepted scale and to understand if the system in its current form is sufficiently usable. This survey will take approximately 3 minutes

**Acceptability E-Scale (AES):** The AES is a 5-item validated measure of the acceptability of mobile interventions, which has a cut-off of 80% for acceptability covering overall and specific component satisfaction. It will take approximately 2 minutes.

**Academic Functioning Outcomes:** Increased academic function is the primary non-usability related goal of the *VetEd* app. Consequently, preliminary educational functioning information related to academic self-efficacy, preparedness for course tasks, and perceived confidence in course completion/retention will also be collected and described. In line with educational research suggesting non-GPA factors can be stronger predictors of educational success and graduation, we will specifically assess self-reported academic self-efficacy using:

- *The Academic Self-Efficacy Scale*(ASES), an eight-item rapid assessment instrument to assess respondent self-efficacy regarding several academic skills related to academic achievement, such as time management, taking notes, taking tests, and general academic ability.
- *The Coping With Education Barriers Subscale*(CWBS), a subscale of the full 28 item scale that includes 2 subscales, the Coping with Career-Related Barriers (not administered for this study) and the Coping with Educational Barriers scale (20 items), assessing participants' degree of confidence in overcoming potential educational barriers (both internal and external).
- We will also assess self-reported confidence in completing coursework and academic retention (qualitative interview).

Both quantitative scales will take approximately 15 minutes. The qualitative interview, which will be combined with the mobile app feedback interview, will take approximately 30 minutes.

**Community Reintegration:** The Military to Civilian questionnaire (M2C-Q) is a 16-item intended to measure dimensions of community reintegration related to productivity (in education, work, and domestic life); social relations; community engagement; and perceived meaning in life, self-care, and leisure. It will take approximately 5 minutes.

**Data Management.** Gesiel Software, Inc. will collect app utilization data for all participants. When data collection is complete, we will lock the database, conduct quality checks, and perform the data analyses described below. Paper research files will be kept at the VA Bedford HCS in a locked cabinet where data will be encoded with deidentified ID numbers and on an encrypted, secure VA server space that will be used solely for this study.

### 3.5 Analysis Plan

**Data analysis plan.** The main Phase 2 quantitative measures of acceptability and usability will be the Acceptability E-Scale and the System Usability Scale (SUS), respectively. We expect that Acceptability E-Scale and SUS ratings will increase across the 3 waves of app revision, and that by the third wave we will reach the benchmark of 80% on the Acceptability E-Scale and a 68 on the SUS (good acceptability). Additional data will be provided by the qualitative interviews after app use, using RAP processes outlined in Phase 1. We will also assess feasibility and engagement by measuring the proportion of

individuals who successfully complete the 4-week app testing, with at least 5 completed activities (of requested 8, 2 per week) or 63% of the program completed, in line with the mean number of completed sessions found in previous mobile interventions for chronic conditions.

We will also assess academic functioning (academic self-efficacy, course task completion, and perceived retention/course completion) and community reintegration (M2C-Q) pre- and post-app use for each student Veteran specifically to 1) characterize the sample in terms of baseline academic functioning and community reintegration, 2) assess for possible changes in academic functioning and community reintegration, and 3) test the feasibility of these measures in anticipation of a larger, future RCT. This assessment will include testing the hypothesis that app use may lead to improvements in academic self-efficacy (ASES) and ability to complete courses tasks (CWBS), or potentially improvements in community reintegration (M2C-Q) mental health symptoms (PCL5, PHQ-9). To evaluate this, we will conduct non-parametric. Within subject statistical analyses between pre and post-app use scores on these two measures (using Wilcoxon Signed Rank Test), which is appropriate for small sample testing and outcomes that may thus not be normally distributed. We will use caution in our interpretation of inferential analyses.

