**Mobile application are a promising way to provide support and resources to those unable or unwilling to access in-person services.** Innovative strategies to reach student Veterans with mental health concerns are needed to circumvent inaccessibility and stigma, in order to increase the acquisition of coping and academic skills. Although one such intervention, Veterans Integration to Academic Leadership-Supported Education (VITAL-SEd; described in further detail below) has shown promise in pilots and RCTs, the typical time from standard in-person treatment development to implementation can take 20 years. Consequently, VA efforts to provide web- and app-based resources for intervention programming have increased. Mobile interventions have the potential to reach Veterans who might otherwise not have access to VA clinical care, as 81% of adults have access to smartphones. Following initial technology development, mobile app interventions are relatively easy to implement within clinical settings compared to in-person

interventions, as they do not require training staff. Once developed, an app to support Veterans' transition to the student role could provide psychoeducation, skill building, and connection to VA services both directly to Veteran users and as a complement to VA-provided services. [However, engagement - both initial and sustained - remains a problem for health apps. Studies suggest that engagement with behavioral apps can be improved by factors including positive perceptions of usefulness, motivation to pursue a goal, and visualizing user data in the app suggesting the importance of Veteran input early in development and testing. Additionally, adoption and engagement of apps may be bolstered if the app is recommended by a source the target user trusts and finds credible, such as VITAL staff. To improve both initial and sustained engagement, both target-use (Veteran) and future app referral sources (e.g., VA staff and college staff) should be involved in development, assessment, and future dissemination planning.

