## 2.2 Preliminary Studies

Our team includes researchers with expertise in student Veterans, technology, and mental health from the VISN 1 Mental Illness Research, Education, and Clinical Center (MIRECC) and the Center for Healthcare Organization and Implementation Research (CHOIR). The core research team includes **PI [name]**, with expertise in educational technologies, student development, and the creation and testing of mobile interventions for mental health, insomnia, and chronic pain; **Co-I [name]**, specialist in Veterans' supported education, career development, and mental health interventions; and **Co-I [name]**, with expertise in development and usability testing of mobile programs for Veterans with mental health concerns. Our project will draw on the following preliminary studies:

**VetSED:** The Veteran Supported Education (VetSED) manualized treatment provided personalized supported education for Veterans with academic goals. A small VetSED RCT pilot was conducted with 33 Veterans with PTSD who had higher education goals. Despite a small sample and matched attention control that could have diluted effects, significant positive differences were found, with the intervention group spending greater amounts of time on educational activities ( $p = 0.002$ ). However, the high intervention attrition rate (30%) suggested difficulties accessing the in-person program.

**VITAL-SED:** The Veterans Integration to Academic Leadership-Supported Education (VITAL-SED) program^32 was developed using psychiatric rehabilitation and supported education principles. Based partially on VetSED, both the pilot trial and RCT (PI: [name]; CO-I's: Drs. [name] and [name]) provided critical data on the particular needs of student Veterans with unmet psychiatric issues. In the pilot study for VITAL-SED, 8 Veterans with mental health disorders (e.g., PTSD, substance use) reported high levels of satisfaction with treatment in relation to perceived academic issues (Table 1). Following this pilot, a larger RCT (n=43) was completed in 2020. Preliminary findings showed that, compared to the control group, Veterans in VITAL-SED reported significant improvement in completing academic tasks ( $p = 0.02$ ), psychosocial functioning ( $p = 0.04$ ), and a reduction in psychiatric symptoms on the PCL-5 ( $p = 0.03$ ) and PHQ-15 ( $p = 0.02$ ).

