**Usability testing procedures.** Following the consent process, participants will complete a series of baselines assessments (approximately 2.5 hours total) related to their academic experiences, technology acceptance, mental health functioning and symptomology, and community integration. Participants will then be provided with the app and log-in information for *VetEd*, with instructions on how to utilize the app at home over a four-week period. During this Phase, we will access information about enrolled participants via their VA Health CPRS and/or VISTA.

such as diagnoses, progress notes, medications, and specific information concerning substance use, to determine how other treatments are influencing outcomes for this study related to their mental health and academic functioning. During that time, they will complete at least two in-app tasks within

per week, with instructions provided specifically about which to access in Weeks 1, 2, 3, and 4. These will include setting up an educational roadmap, tracking course assignments, learning about successful study strategies, completing a coping exercise, and finding information related to GI Bill benefits. There will also be a quick midpoint assessment (45 minutes). Participants will complete surveys following this 4-week app piloting, and to evaluate the app in the following areas: (a) app usefulness: whether users can successfully complete designated tasks on the app, (b) effectiveness: the ability to accomplish assigned educational app tasks quickly and easily, (c) learnability: the ability to meet pre-determined app navigation goals (e.g. accessing and inputting information into the education roadmap), (d) satisfaction: users' feelings and opinions about the app related to their educational functioning and alignment with mental-health needs, and (e) engagement: initial and sustained interaction between a user and a mobile application. Usability measures will include two quantitative system usability scales (SUS; AES), task completion (quantitative), app log-in and use information (engagement). Perceived usefulness, engagement, and overall satisfaction will also be assessed through a post-app qualitative interview (survey + interview will be 2 hours total). After each round of testing (4-5 participants per wave, total n = 15), the investigative team will work with the programming team to improve the app.

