#### **4.5.2 Enrollment:**

60 participants will potentially be consented in the study to reach our goals for participation in focus groups (n = 21) and the formative evaluation, (n=15). A participant will be enrolled in the study immediately after the informed consent process. Participants in the focus group will immediately participate in the focus group after an informed consent process. For participants in the usability pilot testing, participation will take place immediately after an informed consent process.

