  - The study team will not identify, directly or indirectly, any individual participant in any report of such research or otherwise disclose participant identities in any manner.

Following this initial screening, potential study candidates will be consented and then participate in a detailed psychiatric screening interview at the first study visit with trained project staff who are closely supervised by [name]. Effective screening will exclude Veterans who would be at greater risk because of psychiatric conditions revealed by this process. [name] has used the aforementioned screening criteria successfully in the past with behavioral intervention studies. If at any point there are significant adverse reaction during the screening process, the participant will be removed from the study and appropriate treatment implemented. This could include immediate assessment to a local emergency room.

- 4) There is a possibility that study participants will not improve their academic functioning after testing the mobile app. All participants who fail to respond to treatment or withdraw prematurely will be referred for alternative treatment. If withdrawal from the study is necessary, we will provide appropriate alternative treatments (e.g., placing a consult with the VITAL program or Mental Health Clinic). [name] will discuss the study, alternative treatments, or any concerns about the study with participants if requested by the participant or health care provider.
- 5) Participants may possibly experience clinical deterioration during the study. However, [name] will be available to participants by phone, or in person if necessary, to discuss any concerns throughout the treatment period. Drs. [name], [name], and [name] are all licensed psychologists, and will be available to study participants in the event of a clinical emergency; participants may also go to Bedford VA walk-in clinic if a clinical emergency occurs. This will be clearly communicated orally and in writing to study participants. Participants will be withdrawn from the study if their clinical condition deteriorates substantially. Participants may also be withdrawn if, in the judgment of the study investigators, remaining in the study poses a substantial risk to the participant or a higher level of care is needed.

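### Does the wave-3 SUS target of 68 need a written rule for users who leave before the post-app survey?

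*Combined protocol and SAP*

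**What the plan says.** Section 3.5 (Analysis Plan) sets the roles: "The main Phase 2 quantitative measures of acceptability and usability will be the Acceptability E-Scale and the System Usability Scale (SUS), respectively". Ratings are expected to rise over three waves of app revision, and "by the third wave we will reach the benchmark of 80% on the Acceptability E-Scale and a 68 on the SUS (good acceptability". No time point, summary statistic or set of users is named for either benchmark, and there is no rule for a missing score.

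Table 3 in section 3.4 schedules both scales at midpoint and at post-app follow-up. Section 3.3 (Usability testing procedures) says "Participants will complete surveys following this 4-week app piloting". Section 4.7 pays $20 for the midpoint check-in, whose stated purpose is to look for usability problems, and $90 for the follow-up visit.

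Section 3.5 treats completion as a separate outcome: "We will also assess feasibility and engagement by measuring the proportion of" users who finish the four weeks with at least 5 of the 8 requested activities. Sections 3.4 and 3.5 contain no statement that SUS or AES scores are limited to those users.

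**The concern.** A usability score taken only from people who stay with an app can flatter it, because those who find it hard to use may be the ones who leave. The protocol gives reasons to expect some loss. Section 2.1 says "engagement - both initial and sustained - remains a problem for health apps". Section 2.2 reports that in a predecessor programme "the high intervention attrition rate (30%) suggested difficulties accessing the in-person program". Section 4.6.1 (Protection Against Risk) provides that "All participants who fail to respond to treatment or withdraw prematurely will be referred for alternative treatment", but says nothing about their data. Section 4.5.2 adds that "60 participants will potentially be consented in the study to reach our goals for participation in focus groups (n = 21") and 15 in usability testing, without saying whether a user lost after receiving the app is replaced.

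The SUS is the main usability measure and 68 is its only numerical target. If leavers dropped out of the score, wave 3 could appear to reach 68 when the 5 users given the app did not, and part of the expected rise across waves could reflect who stayed. A midpoint SUS is already scheduled, so a remedy seems to be at hand.

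**Working it through.** **The plan's own figures.** 3 waves × 5 users = 15. Focus groups 21 + usability 15 = 36. Completion 5/8 = 62.5%, stated as 63%. All reproduce. No alpha, power, SD or dropout rate is given for the SUS target, so no power calculation applies.

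**How often a wave could lose a score.** Let *a* be the chance that a user gives no post-app SUS, with independent losses. Then P(at least 1 of 5) = 1 − (1 − a)^5 and P(2 or more) = 1 − (1 − a)^5 − 5a(1 − a)^4.

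| a | at least 1 of 5 | 2 or more of 5 |
|---|---|---|
| 10% (assumed) | 41% | 8% |
| 20% (assumed) | 67% | 26% |
| 30% (section 2.2, in-person programme) | 83% | 47% |

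**How far a missing score could move the mean.** Suppose the benchmark is read on a mean. With *k* leavers of mean score L and completers' mean M, the all-user mean is ((5 − k)M + kL)/5. Take M = 70 and L = 58, the lower SUS anchor in section 3.4:

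- k = 1: (4 × 70 + 58)/5 = 67.6
- k = 2: (3 × 70 + 2 × 58)/5 = 65.2

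Both are below 68. But M = 70 is only 2 points above the target. The leaver mean below which the all-user mean falls under 68 is 68 − (5 − k)(M − 68)/k:

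| Completers' mean M | 1 leaver | 2 leavers |
|---|---|---|
| 70 | 60 | 65 |
| 72.5 | 50 | 61.25 |
| 75 | 40 | 57.5 |

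The conclusion therefore depends on how close completers are to 68 and how low leavers would score. The documents give neither.

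**Whether leaving the app means losing the score.** Three provisions bear on this.

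- Section 3.3 has participants complete the post-app surveys and does not restrict this to those who finished the tasks.
- Section 4.7 attaches no app-use condition to the $90.
- Completion in section 3.5 counts activities, not attendance at follow-up. A user with 3 of 8 activities fails that measure and can still give a post-app SUS.

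Only withdrawal from the study or non-attendance loses the score, and no rate for either is given for this study. The 30% comes from an in-person programme, and the protocol attributes it to difficulty of access. The engagement problem in section 2.1 concerns app use, not survey response.

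**Whether lost users would vanish.** No section says that users are replaced within a wave. The 60 consents cover both phases. Section 4.6.1 places the detailed psychiatric screening after consent, so exclusions at that step can account for surplus consents. Section 3.4 collects app use, including the percentage completing the program, and its data management paragraph covers all participants. A shortfall in scores would show against that denominator.

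**The case for a change.** The strongest argument for a change is that it costs little. Two SUS scores per user are planned and the one to be compared with 68 is not named, so time point, summary and denominator could be chosen after the scores are seen. With 5 users that choice can decide which side of 68 the wave falls on. A few sentences and a count table would settle it without new visits. The team recognises survivorship bias for the Phase 1 focus groups in section 3.3, so silence in Phase 2 looks like an oversight.

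Part of this stands: the three items are unnamed, and the arithmetic is right. The rest is weaker.

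- A score collected after four weeks of use is the natural one to hold against an end-of-wave target, and section 4.7 already gives the midpoint visit a different job.
- Substituting the midpoint score for a missing post-app score mixes shorter and longer use of the app, and does nothing for users lost before the midpoint. It is a trade-off, not a clear gain.
- The Phase 1 remark concerns whom to recruit. Phase 2 has its own recruitment safeguard in section 4.4: users must report that they are struggling with current course activities.
- Withdrawal can also follow clinical deterioration (section 4.6.1), which need not reflect usability. That leavers would score lower is plausible but not shown.

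**Conclusion.** No change to the plan is needed. Section 3.5 leaves a missing-score policy unwritten; it does not prescribe a completers-only analysis, and the survey and payment provisions point towards collecting the post-app SUS from people who stop using the app. The same holds for the 80% AES benchmark, which has the same schedule.

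The possible effect is a shift of a few points in a mean of 5 (70 to 67.6 with one leaver, 70 to 65.2 with two). It rests on assumed loss, an assumed leaver score of 58 and completers only 2 points above the target. Nothing turns on the result: 68 is an expectation in a formative wave, with no test and no go/no-go rule, and interviews, task completion and usage data are read beside it.

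With 5 users per wave, an analyst would ordinarily list individual scores, state how many were given the app and how many answered at each assessment, and describe the wave as above or below 68. The present text already allows all of that. The judgement would differ if the documents limited the scores to completers, replaced leavers within a wave or tied a decision to 68. They do none of these.

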### **Primary Aims:**

**Aim 1.** Develop a Veteran-centered educational support app by conducting focus groups [(3 focus groups, n=8, n=8, n=5, total n = 21)] of student Veterans with mental health disorders to identify their perceived academic needs, app preferences, and evaluate Veteran-centered content.

**Aim 2.** Test and iteratively revise the *VetEd* app (3 waves of n= 5, total n =15) by assessing app software, content, human-computer interface, usability, satisfaction data, and preliminary exploration of changes in educational functioning (course activity completion, academic self-efficacy, and retention).

**Hypotheses:** Although we are underpowered to detect statistically significant changes in educational functioning scores, we will utilize non-parametric analyses to assess for potential changes from pre- and post-app use related to academic functioning (academic self-efficacy, course task completion, and perceived retention/course completion) and community reintegration (M2C-Q).

**Secondary Aims:** N/A

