Following the informed consent process, participants will complete a 1.5 hour audio (if in person) or video-recorded (if virtual) focus group. [name] will follow a similar protocol used for previous focus groups for educational interventions (PI: [name]) and mobile apps (PI: [name]). This will include questions assessing Veterans’ reasons for pursuing higher education, exercises they find helpful for learning academic skills (e.g., task management), messages that motivate them to complete course work, barriers related to mental health that impede successful course completion, and potential app resources to improve their academic functioning. Preliminary app content will be presented via PowerPoint and mobile app mock-ups for review and feedback, including discussing additional elements Veterans would find helpful in the app. Interviews will be transcribed by the VA Centralized Transcription Services Program. We will use Rapid Assessment Procedures (RAP), an effective, widely used rapid data collection process. Coding will include the creation of summary points into a data matrix that organizes these points for each main topic of inquiry. This will allow the research team to systematically assess similarities, differences, and trends in responses across the focus groups. Finally, after a discussion of matrix contents, we will create a final memo summarizing findings and noting key themes for content. We will use this information to understand factors that may improve acceptability of a *VetEd* app as well as features to revise or create.

**Phase 2 Pilot Usability Testing (9 months):** The goals of this phase are to: 1) gain feedback on the *VetEd* mobile app via Veteran usability testing; 2) assess Veteran interest, satisfaction, and usability of *VetEd*; 3) iteratively address any technological concerns, and 4) collect preliminary information on the impact of the *VetEd* app on academic functioning (retention, perceived course task ability, and educational self-efficacy) and community reintegration. We will conduct pilot usability testing with 15 Veterans who meet eligibility criteria, conducted in three waves. Each usability testing wave will include 5 participants, based on the finding that approximately 80% of usability problems can be detected using a sample of 4 to 5 participant per wave.

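### Perceived retention or course completion is promised as a pre/post outcome, but its only named source is an unscored interview held after app use

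*Combined protocol and SAP*

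**What the plan says.** The promise is made in three places in the combined protocol and SAP.

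- 3.5 Analysis Plan: "We will also assess academic functioning (academic self-efficacy, course task completion, and perceived retention/course completion) and community reintegration (M2C-Q) pre- and post-app use". The first stated purpose is to "characterize the sample in terms of baseline academic functioning and community reintegration". The second is to look for change, and the third is to try out the measures for a later RCT.
- 1.0, Hypotheses: "we will utilize non-parametric analyses to assess for potential changes from pre- and post-app use related to academic functioning". The outcomes covered are "related to academic functioning (academic self-efficacy, course task completion, and perceived retention/course completion) and community reintegration (M2C-Q".
- 1.0, Aim 2: "preliminary exploration of changes in educational functioning (course activity completion, academic self-efficacy, and retention".

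The measurement is described elsewhere.

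- 3.4, Academic Functioning Outcomes, assigns confidence in finishing coursework and academic retention to a qualitative interview. This is the same interview as the app-feedback one and takes about 30 minutes.
- 3.3 dates that interview: usefulness, engagement and satisfaction "will also be assessed through a post-app qualitative interview (survey + interview will be 2 hours total".
- Table 3 in 3.4 marks the Post-App Interview only at Post-App Follow-up and lists academic outcomes among its purposes.
- 3.5 gives timing and method: "Additional data will be provided by the qualitative interviews after app use, using RAP processes outlined in Phase 1". The Phase 1 description in 3.3 says what that method yields: "Coding will include the creation of summary points into a data matrix that organizes these points for each main topic of inquiry".

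**The concern.** A pre/post assessment needs the same quantity measured twice, and a non-parametric analysis of change needs numbers or ranks at both times. For perceived retention or course completion, the schedule names one occasion, after the app has been used, and a method that produces themes.

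Followed as written, the plan would give post-app themes on this outcome. It would give no baseline description and no paired change, which are the first two purposes in 3.5. The third purpose suffers too, because there is no baseline retention measure to try out.

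The gap cannot be closed later. Once a participant has used the app, a pre-app rating can only be recalled, not observed. The outcome is not incidental: 3.4 treats better academic functioning as the app's main goal apart from usability, and 2.3 says the project is meant to lead to a larger RCT.

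**Working it through.** The plan gives no figure to reproduce, so the check is a trace. Each outcome in the 3.5 sentence is followed to its named source, its time points in Table 3, and its score.

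| Outcome in 3.5 | Named source | Baseline | Post-app | Score |
|---|---|---|---|---|
| Academic self-efficacy | ASES | yes | yes | yes |
| Course task completion | CWBS (by the 3.5 hypothesis sentence) | yes | yes | yes, as confidence |
| Perceived retention or course completion | qualitative interview (3.4) | none listed | yes | none defined |
| Community reintegration | M2C-Q | yes | yes | yes |

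Three outcomes have a scored instrument at both visits and one does not: 3 + 1 = 4. Phase 2 has 3 waves of 5, so 3 × 5 = 15 participants. Scheduled pre/post pairs on retention: 0 of 15.

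**Could another source supply the baseline?**

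- The ASES is described as self-efficacy for academic skills and the CWBS as confidence against educational barriers. 3.4 lists retention as a separate item beside them.
- App-utilization data cover minutes, logins and in-app activities, none of which exist before app use.
- 4.4 requires current enrolment in at least two courses, so enrolment status has a known starting point. The perceived rating does not.

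**Is Table 3 the full baseline content?** Not certainly. 3.3 describes baseline assessments on academic experiences and on technology acceptance, and the latter has no row in Table 3. The timed baseline measures in 3.4 are demographics 10, PHQ-9 and PCL-5 7, SCID-5 30, ASES and CWBS 15, and M2C-Q 5. They sum to 10 + 7 + 30 + 15 + 5 = 67 minutes, against about 2.5 hours (150 minutes). That leaves room for unlisted items, although no retention item is named anywhere.

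**Does a specified test fail?** No. The hypothesis sentence in 3.5 names the ASES, CWBS, M2C-Q, PCL5 and PHQ-9, and the Wilcoxon sentence after it refers to two measures. Retention is in neither. The conflict is with the pre/post wording in 3.5 and with the non-parametric analysis of change in 1.0.

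**The case against.** The strongest reply is that the operative text is consistent. 3.4 assigns retention to an interview and says the academic information will be collected and described. Table 3 labels the interview as post-app, and the Wilcoxon sentence leaves retention out. On that reading, retention was always post-app, qualitative and descriptive, and the pre/post wording is only a loose umbrella list. This narrows the point but does not remove it. The umbrella sentences are the plan's own statement of what will be assessed and why, and 1.0 names this outcome explicitly under non-parametric change.

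It can also be said that the interview might ask about perceived change. The interview guide is not in the documents, so this is possible. A recalled change is still not a baseline, and it does not give a paired score.

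A reader might infer more than the documents support:

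- **That nothing about retention will be asked at baseline.** The wider baseline content in 3.3 means only a gap in specification is shown.
- **That a planned test cannot be run.** No test specified in 3.5 depends on retention.
- **That course task completion has no instrument.** The Phase 2 goals in 3.3, the outcome text in 3.4 and the hypothesis in 3.5 describe that outcome as perceived ability or preparedness, and the CWBS is scheduled at Baseline, Midpoint and Follow-up. What remains is a label in 1.0 and 3.5 that says completion where the instrument measures confidence.

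**Conclusion.** The point holds for perceived retention or course completion. The documents promise a baseline description and a pre/post change, and they specify neither a baseline nor a score. This affects one of the four outcomes in the 3.5 sentence, for all 15 planned Phase 2 participants.

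Severity is minor to moderate. The study is an uncontrolled pilot that declares itself underpowered and promises cautious interpretation. Its main quantitative measures, the SUS and AES, and the app-completion benchmark do not depend on this outcome.

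The conclusion assumes that the interview in 3.4 is the only source for this outcome, as the documents indicate. If an unlisted baseline questionnaire already contains a scored retention item that is repeated after app use, naming it in 3.4 and Table 3 would settle the matter.

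**What to change.** Choose one option before the first Phase 2 baseline visit.

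**Option A: measure it twice.** Add one scored self-rating of confidence in completing current courses and staying enrolled (for example 0 to 10) at Baseline and Post-App Follow-up, with its own row in Table 3. Report the individual pairs and the median change descriptively, and say in 1.0 that this item is described, not tested. Assuming about 1 minute per visit, the timed measures go from 67 to 68 of 150 minutes at baseline. At follow-up they go from 7 + 3 + 2 + 15 + 5 + 30 = 62 to 63 of 120 minutes (PHQ-9 and PCL-5, SUS, AES, ASES and CWBS, M2C-Q, interview). The remaining time is not claimed to be spare. The drawback is that the item would be unvalidated and coarse.

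**Option B: withdraw the pre/post claim.** Remove retention and course completion from the pre/post statements in 1.0 (Aim 2 and Hypotheses) and 3.5, and report them as post-app qualitative findings only. This changes wording alone. The drawback is that the later RCT gets no change information on this outcome.

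**Terminology, under either option.** In 1.0 and 3.5, relabel course task or activity completion to match the perceived-ability wording used elsewhere, and report the CWBS as confidence in overcoming educational barriers. No new course-task item is needed.
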